4 ANALYSIS SETS

4.1 Full Analysis Set (FAS)

The FAS is defined as all randomized subjects. Subjects will be included in the treatment group to which they were randomized, regardless of the treatment they actually received. All efficacy analyses will be performed on the FAS.

4.2 Safety Set

The safety set is defined as all randomized subjects who received at least one dose of study drug. For summaries and listings where treatment group is included, subjects will be included in the treatment group to which they were actually treated. All safety analyses will be performed on the Safety Set.

4.3 Plasma PK Set

The plasma PK set is defined as all randomized subjects who received at least one dose of study drug and who have a blood sample collected to assess LYC-30937 and/or its metabolite (LYC-53552) concentrations. For listings where treatment group is included, subjects will be included in the treatment group to which they were actually treated.

4.4 Skin PK Set

The skin PK set is defined as the subset of all randomized subjects who received at least one dose of study drug and who have a skin biopsy sample collected to assess LYC-30937 concentrations. For listings where treatment group is included, subjects will be included in the treatment group to which they were actually treated.

4.5 Protocol Deviations and Treatment Misallocations

The list of major and minor protocol deviations will be determined while the data are still blinded, prior to database lock. The list will be prepared and maintained by clinical CRO, reviewed by Lycera team for major/minor classification and submitted for inclusion in the clinical database (SDTM.PD) as an Excel file. Protocol deviations will be used to assess the

quality of study conduct but there are no plans to use them to define an additional population for analyses. Treatment misallocation will be handled as described below.

Efficacy data will be summarized “as randomized,” meaning the subject will be summarized under the treatment they were randomized to, regardless of what treatment was actually received.

Safety, PK and skin biopsy data will be summarized “as treated,” meaning the subject will be summarized based on the treatment that was actually received.

5 ANALYSIS PLAN OVERVIEW

5.1 General Methodology

Continuous safety and efficacy endpoints will be summarized using mean, standard deviation, median, minimum, and maximum. Discrete safety and efficacy endpoints will be summarized by the number and percentage of subjects in each category. Continuous efficacy endpoints will be analyzed using an analysis of covariance model with treatment as a factor and baseline value as a covariate. Discrete variables will be analyzed using a chi-square test.

The primary efficacy endpoint will be analysed using a 2-sided significance level $\alpha = 0.05$. All secondary and exploratory efficacy endpoints will also be analysed using 2-sided $\alpha = 0.05$ level of significance. The p-values for the secondary and exploratory endpoints will be considered descriptive and no adjustments will be made for multiplicity.

The analysis of Safety endpoints will be limited to descriptive statistics and by subject listings.

Concentrations of LYC-30937 in plasma and skin tissue will be limited to listings.

5.2 Statistical Power and Sample Size Considerations

A total of approximately 30 subjects will be randomized into the study and using a 2:1 randomization ratio of LYC-30937-EC 25 mg or placebo daily.

A sample size of 30 subjects (20 LYC-30937-EC and 10 placebo) will achieve approximately an 80% power to detect difference in the mean percent change from baseline in PASI at Week 12 in the LYC-30937-EC treatment group compared to the placebo treatment group. The mean percent change from baseline in PASI at Week 12 in the placebo treatment group is assumed to be 16.7% with SD=32.0. The power was

computed assuming the mean percent change from baseline in PASI at Week 12 in the LYC-30937-EC treatment group is at least 52.7% (SD=32.0) for a mean difference of at least 36.0%. The test statistic used is the two-sided t-test. The alpha level of the test was targeted at 0.05.

5.3 Baseline Definition

For efficacy analyses, baseline is the last assessment (including unscheduled visits) obtained before the randomization. All assessments obtained after randomization are considered as post-baseline unless otherwise specified.

For safety analyses, baseline is the last assessment (including unscheduled visits) obtained before the first dose of study treatment. All assessments obtained after the first dose of study treatment are considered as post-baseline unless otherwise specified.

Re-randomization will not be used for baseline definition and only one baseline value will be defined referring to the first randomization.

5.4 Change from Baseline

Change from baseline (CFBL) will always be calculated as (post-baseline – baseline). It will be calculated for Subjects with both a baseline and post-baseline value as applicable.

If a baseline value has not been recorded for a parameter, then CFBL will not be calculated for that parameter, and the subject will be excluded from CFBL analysis.

Percent CFBL is the CFBL divided by the baseline value multiplied by 100. Subjects with a value of 0 at baseline or with no baseline value recorded cannot have percent CFBL calculated and they will be excluded from percent CFBL analysis.

5.5 End of Treatment Value

For Safety parameters, the end of treatment value is defined as the last value collected for each subject excluding the follow-up visit.

5.6 Visit Windows

Data at scheduled visits will be assigned to analysis visits as defined in the Visit Window table below. To ensure that all visits have the possibility to be included in the summaries, the visit window will also classify all unscheduled and early termination visits. The analysis visits will be derived in terms of study days since the first dose of study

treatment for safety assessments, or since the date of randomization for efficacy assessments. These analysis visits will be utilized in the summary and analyses of efficacy and safety endpoints.

If a subject has more than 1 assessment in a visit window, only the assessment that is closest to the Scheduled Visit Day will be used for analysis. In case 2 assessments have the same distance from the Scheduled Day, the later assessment will be used for analysis. The early termination visit will be assigned to an analysis visit based on the window below.

Separate visit window tables are provided based on how frequently the assessments were done. For assessment which has only 1 scheduled post-baseline assessment, say at Week 12, Scheduled Visit Day will be similar as either of the tables below with visit window upper limit of Day 92, and all previous rules will apply.

No visit windows will be applied for summaries of the follow-up period data.

Table 1 Visit Windows for Assessments Done at Baseline and Weeks 2, 4, 8, and 12

Analysis Visit	Scheduled Visit Day	Visit Window for Summarization
Baseline	Day 1	≤ Day1
Week 2	Day 15	Day 2 – Day 22
Week 4	Day 29	Day 23 – Day 43
Week 8	Day 57	Day 44 – Day 71
Week 12	Day 85	Day 72 – Day 92

Table 2 Visit Windows for Assessments Done at Baseline and Weeks 4, 8, and 12

Analysis Visit	Scheduled Visit Day	Visit Window for Summarization
Baseline	Day 1	≤ Day1
Week 4	Day 29	Day 2 – Day 43
Week 8	Day 57	Day 44 – Day 71
Week 12	Day 85	Day 72 – Day 92

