6.4.4 Laboratory Assessments

Laboratory assessments will be performed at the time points indicated in the schedule of assessments (Table 1) and will be evaluated by a central laboratory.

The PI at the site must assess the clinical significance of all laboratory values outside the laboratory reference ranges. All laboratory abnormalities considered to be clinically significant by the PI should be repeated. Confirmed, clinically significant laboratory abnormalities should be further evaluated by the PI and captured as an AE.

Chemistry Panel Sample

The chemistry panel includes: glucose, calcium, sodium, albumin, total protein, potassium, bicarbonate, chloride, blood urea nitrogen (BUN), creatinine, lactate, lactate dehydrogenase (LDH), alanine aminotransferase (ALT), aspartate aminotransferase (AST), reflexive bilirubin (total, direct, indirect), alkaline phosphatase (ALP), cholesterol, triglycerides, creatine phosphokinase (CPK), high sensitivity C-reactive protein (hsCRP), high density lipoprotein (HDL), and low density lipoprotein (LDL).

Hematology Panel Sample

The hematology panel includes: platelets, WBCs with differential if abnormal (% and absolute counts), hematocrit, red blood cells (RBCs), hemoglobin, mean corpuscular volume (MCV), mean corpuscular hemoglobin concentration (MCHC), and mean corpuscular hemoglobin (MCH).

LYC-30937

Clinical Protocol LYC-30937-2003

Issue Date: 30 August 2016

Urine Sample (Dipstick)

The urinalysis test includes: color, appearance, specific gravity, leukocyte esterase, pH, protein, glucose, ketones, blood, and nitrates. Microscopic urinalysis will be performed on samples with abnormal blood, leukocyte esterase, protein, and nitrate. This test will be evaluated by dipstick at the central laboratory.

Childbearing Potential Evaluation and Pregnancy Tests

Serum FSH in postmenopausal female subjects and a serum hCG (pregnancy test) in premenopausal females will be evaluated at the central lab at screening.

Urine pregnancy tests for female subjects of childbearing potential will be performed at the time points indicated in the schedule of assessments (Table 1).

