6.4.6 Monitoring Subjects for Adverse Events of Special Interest

Subjects will be monitored throughout the study for the occurrence of AEs and for abnormal clinical laboratory values.

LYC-30937

Clinical Protocol LYC-30937-2003

Issue Date: 30 August 2016

AEs of special interest include those that may be related to LYC-30937's mechanism of action of mitochondrial modulation and those AEs which may indicate hepatotoxicity. Investigators should be particularly mindful of these AEs, which include vomiting, abdominal pain, elevated lactate, and abnormal liver function tests indicative of possible hepatotoxicity (AST, ALT, total bilirubin, ALP, LDH). Guidance for monitoring for these AEs of special interest is outlined below:

Vomiting or Abdominal Pain:

If a subject exhibits repeated episodes of vomiting or persistent abdominal pain they must contact their investigator. They should present to the clinic as soon as possible to be evaluated for potential source of the symptom and liver function testing should be performed. The study medical monitor should be contacted. If a source is not readily identified then study drug should be withheld and the subject should continue to be evaluated for the source and managed as medically indicated. Study drug may be re-started if it has been interrupted for no more than 3 days and the source of the vomiting or abdominal pain is determined, or if these symptoms resolve, and in the clinical judgement of the investigator and study medical monitor it is safe for the subject to continue study drug. If the subject is off drug for more than 3 days the investigator should withdraw the subject from the study.

Monitoring Lactate and Liver Function:

If a subject exhibits any of the following elevations, study drug should be withheld at least until evaluation of the subject:

- ALT or AST > 8 x ULN
- ALT or AST > 5 x ULN for more than 2 weeks
- ALT or AST > 3 x ULN and total bilirubin > 2 x ULN
- ALT or AST > 3 x ULN with appearance of fatigue, nausea, vomiting, right upper quadrant pain or tenderness, fever, rash and/or eosinophilia (> 5%)
- ALP > 1.5 x ULN
- Lactate \geq 3 mmol/L
- LDH > 2 x ULN

If any of the above occur the investigator must contact the subject to request the stop taking study drug and report to the clinic as soon as possible for evaluation (do not wait for the next

LYC-30937

Clinical Protocol LYC-30937-2003

Issue Date: 30 August 2016

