scheduled study visit). As dehydration and heavy physical exertion can cause elevations (eg, of blood lactate levels), the clinical lab should be repeated with the subject instructed to ensure hydration and avoid heavy physical activity. The study medical monitor should be contacted to discuss the case. If the elevation is confirmed by repeat lab and neither dehydration nor physical exertion explains the elevation, study drug must continue to be withheld. Close observation of the subject should be initiated. Repeat liver enzyme and serum bilirubin testing should be performed 2 to 3 times weekly until values return to baseline. Frequency of this retesting can decrease to once per week or less if abnormalities stabilize or the study drug has been discontinued and the subject is asymptomatic. The investigator should obtain a detailed history of symptoms, prior or concurrent diseases, concomitant drug use, alcohol use, recreational drug use, special diets, and exposure to environmental chemical agents. Evaluation should be performed to rule out acute viral hepatitis types A, B, C, D and E; autoimmune or alcoholic hepatitis; nonalcoholic steatohepatitis; hypoxic/ischemic hepatopathy; and biliary tract disease. Obtain additional tests to evaluate liver function as appropriate (eg, international normalized ratio, direct bilirubin). Consider gastroenterology or hepatology consults. If a source of the abnormal value is not readily identified the subject should continue to be evaluated for the source and managed as medically indicated. Study drug may be re-started if study drug has been interrupted for no more than 3 days and the source of the abnormal value(s) is determined, or if upon repeating the clinical lab the value returns to normal, and in the clinical judgement of the investigator and study medical monitor it is safe for the subject to continue study drug. If study drug cannot be ruled out as the cause of the abnormal value then study drug should be permanently discontinued. Additionally, if study drug is interrupted for more than 3 days, then study drug should be permanently discontinued.

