6.6 Clinical Laboratory

Clinical labs are reported for hematology, chemistry, and urinalysis and they include the following parameters:

- **Chemistry:** glucose, calcium, sodium, albumin, total protein, potassium, bicarbonate, chloride, blood urea nitrogen (BUN), creatinine, lactate, lactate dehydrogenase (LDH), alanine aminotransferase (ALT), aspartate aminotransferase (AST), reflexive bilirubin (total, direct, indirect), alkaline phosphatase (ALP), cholesterol, triglycerides, creatine phosphokinase (CPK), high sensitivity C-reactive protein (hsCRP), high density lipoprotein (HDL), and low density lipoprotein (LDL).
- **Hematology:** platelets, white blood cells (WBCs) with differential if abnormal (% and absolute counts), hematocrit, red blood cells (RBCs), hemoglobin, , mean corpuscular volume (MCV), mean corpuscular hematocrit concentration (MCHC), and mean corpuscular hematocrit (MCH).

- **Urinalysis:** color, appearance, specific gravity, leukocyte esterase, pH, protein, glucose, ketones, blood, and nitrates. Microscopic urinalysis will be performed on samples with abnormal blood, leukocyte esterase, protein, and nitrate.

Hematology and chemistry are collected at Screening, Week 2, Week 4, Week 8, Week 12, and at Week 14 (follow-up). Values and change from baseline will be summarized by visit, for the end of treatment visit, and for the overall worst value post-baseline (which includes unscheduled visits), within each treatment group. Appendix 5 provides the directionality of the worst values for each laboratory parameter.

Urinalysis is collected at Screening and Week 12. Results will be listed by subject.

Out-of-range values will be assessed through shift tables. Each lab value will be assessed as low, normal or high based on the normal ranges provided by the central lab. Frequencies of each combination of shifts from baseline to post-baseline visits will be provided by treatment group for hematology and chemistry lab parameters only. Separate by subject listings will also be produced and out-of-range values will be flagged.

Over the course of the study, there may be some labs tests performed that were not mentioned in the protocol. These tests will not be summarized but will be included in the listings and flagged as non-protocol tests.

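### For laboratory data, SAP 5.6 can let a repeat sample replace the abnormal value that prompted it when the visit was early, and no worst-value shift table is planned to catch this

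*SAP*

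**What the plan says.** SAP 5.6 (Visit Windows) assigns data to analysis visits and states that "the visit window will also classify all unscheduled and early termination visits". Unscheduled samples therefore compete with scheduled ones. Within a window, "only the assessment that is closest to the Scheduled Visit Day will be used for analysis", and the tie rule reads: "In case 2 assessments have the same distance from the Scheduled Day, the later assessment will be used for analysis". The scope includes safety: "These analysis visits will be utilized in the summary and analyses of efficacy and safety endpoints".

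Repeat samples are expected. Protocol 6.4.4 states: "All laboratory abnormalities considered to be clinically significant by the PI should be repeated". It says nothing there about stopping drug. For the listed ALT/AST, ALP, lactate and LDH limits, Protocol 6.4.6 adds that "study drug should be withheld at least until evaluation of the subject". The subject is to come in without waiting for the next visit, and "the clinical lab should be repeated with the subject instructed to ensure hydration and avoid heavy physical activity".

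SAP 6.6 (Clinical Laboratory) summarises values and changes by visit, at end of treatment, and for the worst post-baseline value with unscheduled visits included. Its categorical display is the shift table: "Frequencies of each combination of shifts from baseline to post-baseline visits will be provided by treatment group". Out-of-range values are flagged in by-subject listings. No shift to the worst value is stated.

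**The concern.** A nearest-day rule is harmless when extra samples are taken for reasons unrelated to the result. Here an extra sample is often taken because the scheduled one was abnormal. If the repeat wins the window, the abnormal result drops out of the by-visit mean and the visit-level shift table, and a sample taken after evaluation, and sometimes after drug was withheld, stands in its place.

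The shift table is where a reader would look for the number of subjects in each arm who moved out of range. The tests concerned include lactate and liver function, which Protocol 6.4.6 names among the adverse events of special interest. With about 20 active and 10 placebo subjects, one subject is 5% or 10% of an arm.

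**Working it through.** The documents give no figure on this point, so there is none to reproduce. The check applies the SAP 5.6 rule to each permitted visit day.

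**Inputs.** Permitted timing (Protocol 6.1 and Table 1): ±2 days at Weeks 2 and 4, ±3 days at Weeks 8 and 12. Analysis windows (SAP 5.6, Table 1): Days 2-22, 23-43, 44-71 and 72-92 around scheduled Days 15, 29, 57 and 85. Every repeat that can win, by the counts below, falls inside the same window as its trigger.

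**Condition.** Let the visit fall d days from the scheduled day (negative if early) and the repeat r days later. The repeat is used if |d + r| ≤ |d|, the equality coming from the tie rule. For d ≥ 0 no r ≥ 1 satisfies this, so an on-time or late visit keeps its value. For d = −k it gives r ≤ 2k.

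- Weeks 2 and 4: 1 day early, repeat within 2 days; 2 days early, within 4.
- Weeks 8 and 12: 1 day early, within 2 days; 2 days early, within 4; 3 days early, within 6.

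**Example.** The Week 8 sample on Day 54 is abnormal and meets a Protocol 6.4.6 limit, drug is withheld, and the repeat on Day 57 is normal. The distances are 3 and 0 days, so Day 57 is the Week 8 value.

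**Share of permitted visit days on which the repeat wins**, assuming all are equally likely:

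| Lag to repeat | Weeks 2, 4 (5 days) | Weeks 8, 12 (7 days) |
|---|---|---|
| 1-2 days | 2/5 = 40% | 3/7 = 43% |
| 3-4 days | 1/5 = 20% | 2/7 = 29% |
| 5-6 days | 0 | 1/7 = 14% |
| 7 or more days | 0 | 0 |

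The lag is an assumption, since the documents do not state one. Spread evenly over 1-2, 1-3 or 1-7 days, it gives these shares:

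- Weeks 2 and 4: 4/10 = 40%, 5/15 = 33% or 6/35 = 17%.
- Weeks 8 and 12: 6/14 = 43%, 8/21 = 38% or 12/49 = 24%.

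Where there are several repeats, the lag of the first decides whether the trigger is displaced.

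**Size in a table (assumed case).** If one of 20 active subjects has 3, 5 or 8 × ULN replaced by 1 × ULN, that visit's arm mean falls by (3−1)/20 = 0.10, (5−1)/20 = 0.20 or (8−1)/20 = 0.35 × ULN. One subject (1/20 = 5%) can leave the high cell.

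**After the fix.** If the scheduled sample takes precedence, a later repeat displaces it on 0 of 5 and 0 of 7 permitted days.

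**The case against.** A reader might infer that these tables understate drug-related abnormalities as a matter of course, or that the rule removes the very values that led to repeats. The documents do not support that, for these reasons, all of which stand:

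- Replacement needs an early visit and a prompt repeat. Even at a lag of 1-2 days, 3/5 or 4/7 of triggering values are kept.
- Samples go to a central laboratory, and the subject must then be contacted and return, so very short lags cannot be taken for granted.
- The shares bound replacement, not lost shifts. A repeat that is still high still counts as high, and Protocol 6.4.6 foresees elevations that persist over repeated testing.
- The repeat is off drug by rule only for the Protocol 6.4.6 limits. Other repeats may be on drug.
- Some displaced values will be transient. Protocol 6.4.6 itself cites dehydration and exertion as causes.
- The rule is blind to arm and direction. It distorts the comparison only if repeats are more frequent in one arm, and an abnormal unscheduled value can also replace a normal scheduled one.

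It can also be said that nothing is lost from the report. The worst-value summary shows each arm's extreme, the listings flag every out-of-range value for about 30 subjects, and confirmed clinically significant abnormalities become adverse events, tabulated by arm and maximum grade under SAP 6.5. This weakens the point but does not remove it. The worst-value summary is continuous and does not count subjects. The adverse event route depends on confirmation, so an abnormality that is normal on repeat may drop out of the visit-level shift table and also not be recorded as an event.

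**Conclusion.** The concern holds as a possibility built into the rule, not as a general bias. By-visit laboratory means and shift tables can understate abnormalities when a scheduled visit is k days early (up to 2 at Weeks 2 and 4, up to 3 at Weeks 8 and 12) and the repeat comes within 2k days. Replacement shares run from 43% down to zero, depending on week and lag. They rest on visit days uniform over the permitted range and on an assumed lag. The share of shift cells that actually change is no larger and cannot be computed from the documents.

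The remaining gap is that no by-arm count of subjects out of range at their worst value is planned for laboratory data. Safety analysis is descriptive and the peaks stay in the report, so this is a worthwhile, inexpensive improvement and not a threat to the trial's conclusions.

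**What to change.** - **SAP 6.6:** add a shift table by treatment group from baseline to the worst post-baseline value for hematology and chemistry. Include unscheduled samples and use the Appendix 5 directions, with two shifts where Appendix 5 names both the highest and the lowest value.
- **SAP 5.6:** for laboratory by-visit summaries and shift tables, use the scheduled-visit sample, and take an unscheduled one only if the scheduled sample is missing.

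Vital signs need no change: SAP 6.7 already reports the overall post-baseline incidence of clinically notable values with unscheduled visits included.

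The cost is one extra table and a line of SAP wording. The downside is that some transient, unconfirmed abnormalities will be counted in the new table; a footnote can say so.
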